4.3. Protocol Deviations

A by-subject listing will be provided for those subjects who did not meet at least 1 eligibility (inclusion or exclusion) criterion. The listing will present the eligibility criterion (or criteria if more than 1 deviation) that subjects did not meet and related comments, if collected.

Protocol deviations occurring after subjects entered the study are documented during routine monitoring. A by-subject listing will be provided for those subjects with important protocol deviation.

4.4. Assessment of COVID-19 Impact

This study was ongoing during the novel coronavirus (COVID-19) pandemic which has an impact on the study conduct. Some subjects were unable to attend onsite visits due to shelter in place guidelines, site closures, or other reasons. This section describes how special situations due to COVID-19 will be handled in the analysis.

4.4.1. Protocol Deviations Due to COVID-19

A by-subject listing will be provided for subjects with important protocol deviations related to COVID-19, if applicable. A separate listing will be provided for subjects with non-important protocol deviations related to COVID-19, if applicable.

5. BASELINE CHARACTERISTICS

5.1. Demographics and Baseline Characteristics

Subject demographic variables (ie, age, sex, race, and ethnicity) and baseline characteristics (body weight [in kg], height [in cm], body mass index [BMI; in kg/m²]) will be summarized using descriptive statistics for continuous variables and using number and percentage of subjects for categorical variables. The summary of demographic data will be provided for the Safety Analysis Set.

A by-subject demographic listing, including the informed consent date, will be provided by subject ID number in ascending order.

5.2. Other Baseline Characteristics

Other baseline characteristics include:

- UDCA use (yes or no, based on concomitant medication page)
- ALP, GGT, ALT, AST
- Total bilirubin, direct bilirubin, albumin, INR
- Fasting bile acids
- MELD score, Child-Pugh (CP) score
- ELF™ score and components
- FibroSURE/FibroTest® and selected components
- Liver Stiffness Assessed by FibroScan
- Platelets
- Inflammatory bowel disease (IBD) history (yes or no, based on medical history data)
- Ulcerative colitis (UC) history (yes or no, based on medical history data)
- Crohn's disease history (yes or no, based on medical history data)

These baseline characteristics will be summarized using descriptive statistics for continuous variables and using number and percentage of subjects for categorical variables. The summary of these baseline characteristics will be provided for the Safety Analysis Set. No formal statistical testing is planned.

A by-subject listing of other baseline characteristics will be provided by subject ID number in ascending order.

5.3. Medical History

General medical history data will be collected at screening and listed only. General medical history data will not be coded.

cc

[REDACTED]

CCI

7. SAFETY ANALYSES

7.1. Adverse Events and Deaths

7.1.1. Adverse Event Dictionary

Clinical and laboratory AEs will be coded using the current version of the Medical Dictionary for Regulatory Activities (MedDRA). System organ class (SOC), high-level group term (HLGT), high-level term (HLT), preferred term (PT), and lower-level term (LLT) will be provided in the AE dataset.

7.1.2. Adverse Event Severity

Adverse events are graded by the investigator as Grade 1, 2, 3, 4, or 5 according to toxicity criteria specified in the protocol. The severity grade of events for which the investigator did not record severity will be categorized as “missing” for tabular summaries and data listings. The missing category will be listed last in summary presentation.

7.1.3. Relationship of Adverse Events to Study Drug

Related AEs are those for which the investigator selected “Related” on the AE CRF to the question of “Related to Study Treatment.” Relatedness will always default to the investigator’s choice, not that of the medical monitor. Events for which the investigator did not record relationship to study drug will be considered related to study drug for summary purposes. However, by-subject data listings will show the relationship as missing.

7.1.4. Serious Adverse Events

Serious adverse events (SAEs) will be identified and captured as SAEs if the AEs met the definitions of SAEs that were specified in the study protocol. Serious adverse events captured and stored in the clinical database will be reconciled with the SAE database from the Gilead Global Patient Safety Department before data finalization.

7.1.5. Treatment-Emergent Adverse Events

7.1.5.1. Definition of Treatment-Emergent Adverse Events

Treatment-emergent adverse events (TEAEs) are defined as 1 or both of the following:

- Any AEs with an onset date on or after the study drug start date and no later than 30 days after permanent discontinuation of study drug
- Any AEs leading to premature discontinuation of study drug

7.1.5.2. Incomplete Dates

If the onset date of the AE is incomplete and the AE stop date is not prior to the first dosing date of study drug, then the month and year (or year alone if month is not recorded) of onset determine whether an AE is treatment emergent. The event is considered treatment emergent if both of the following 2 criteria are met:

- The AE onset is the same as or after the month and year (or year) of the first dosing date of study drug, and
- The AE onset date is the same as or before the month and year (or year) of the date corresponding to 30 days after the date of the last dose of study drug.

An AE with completely missing onset and stop dates, or with the onset date missing and a stop date later than the first dosing date of study drug, will be considered to be treatment emergent. In addition, an AE with the onset date missing and incomplete stop date with the same or later month and year (or year alone if month is not recorded) as the first dosing date of study drug will be considered treatment emergent.

7.1.6. Summaries of Adverse Events and Deaths

Treatment-emergent AEs will be summarized based on the Safety Analysis Set.

A brief, high-level summary of the number and percentage of subjects who experienced at least 1 TEAE in the categories described below will be provided. All deaths observed in the study will also be included in this summary.

- TEAE
- TEAEs with Grade 2 or higher
- TEAEs with Grade 3 or higher
- TE treatment-related AEs
- TE treatment-related AEs with Grade 2 or higher
- TE treatment-related AEs with Grade 3 or higher
- TE SAEs
- TE treatment-related SAEs
- TEAEs leading to premature discontinuation of study drug
- TEAEs leading to temporary interruption of study drug
- Death

The number and percentage of subjects who experienced at least 1 TEAE will be provided and summarized by SOC and PT for the AE categories described below:

- TEAE
- TEAEs with Grade 2 or higher
- TE treatment-related AEs
- TE SAEs
- TEAEs leading to premature discontinuation of study drug
- TEAEs leading to temporary interruption of study drug

Summaries of all TEAEs by PT only, and by SOC, PT, and maximum severity will also be provided.

Multiple events will be counted only once per subject in each summary. Adverse events will be summarized and listed first in alphabetic order of SOC (if applicable), and then by PT in descending order of total frequency within each SOC. For summaries by severity grade, the most severe grade will be used for those AEs that occurred more than once in an individual subject during the study.

In addition, data listings will be provided for the following:

- All AEs, indicating whether the event is treatment emergent
- All TEAEs with severity of Grade 2 or higher
- All SAEs
- All deaths
- All AEs leading to premature discontinuation of study drug
- All AEs leading to temporary interruption of study drug

7.2. **Laboratory Evaluations**

Laboratory data collected during the study will be analyzed and summarized using both quantitative and qualitative methods. Summaries of laboratory data will be provided for the Safety Analysis Set and will include data collected up to the last dose of study drug plus 30 days. The analysis will be based on values reported in conventional units. When values are BLQ, they will be listed as such, and the closest imputed value will be used for the purpose of calculating summary statistics as specified in Section 3.6. Hemolized test results will not be included in the analysis, but they will be listed in by-subject laboratory listings.

A by-subject listing for laboratory test results will be provided by subject ID number and visit in chronological order for hematology, eGFR, serum chemistry, coagulation, and urinalysis separately. Values falling outside of the relevant reference range and/or having a severity grade of 1 or higher on the Common Toxicity Criteria for Adverse Events (CTCAE) severity grade as described in [Appendix 2](#) will be flagged in the data listings, as appropriate.

No formal statistical testing is planned.

7.2.1. Summaries of Numeric Laboratory Results

Descriptive statistics for laboratory tests will not be provided.

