8.1.2. Primary Endpoint

The primary endpoint is the safety and tolerability of CILO in subjects with PSC and cirrhosis. The safety and tolerability of CILO will be evaluated by examining treatment-emergent adverse events (TEAEs), including SAEs, clinical laboratory tests, and vital signs assessments at various time points during the study.

CCI

█

█

█

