8.5.3. Laboratory Evaluations

Selected laboratory data will be summarized (n, mean, SD, median, Q1, Q3, minimum, and maximum) by study visit along with the corresponding change from baseline values.

Graded laboratory abnormalities will be defined using the grading scheme in the CTCAE Version 5.0 (see [Appendix 3](#)). Grading of laboratory abnormalities for analysis purposes will be performed by the central laboratory.

Incidence of treatment-emergent laboratory abnormalities, defined as values that increase at least 1 toxicity grade from baseline at any time from baseline up to and including the date of last dose of study drug plus 30 days will be summarized by overall. If baseline data are missing, then any graded abnormality (ie, at least a Grade 1) will be considered treatment emergent.

Laboratory abnormalities that occur before the first dose of study drug or after the subject has been discontinued from treatment for at least 30 days will be included in a data listing.

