8.5.4. Other Safety Evaluations

Vital sign measurements and 12-lead ECG data will be summarized by overall and listed by subject.

CCI

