2.3. Changes from Protocol-Specified Analysis

Due to limited subject enrollment in the study, part of safety summaries and listings (body weight, vital signs, prior and concomitant medications, electrocardiogram [ECG], and pharmacodynamic parameters) planned in the protocol will not be provided.

PSC Patient-Reported Outcome (PRO) is a novel endpoint. CCI [REDACTED]

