7.2.2.2. Summaries of Laboratory Abnormalities

Laboratory data that are categorical will be summarized using the number and percentage of subjects in the study with the given response at baseline and each scheduled postbaseline visit.

The following summaries (number and percentage of subjects) for treatment-emergent laboratory abnormalities will be provided by lab test; subjects will be categorized according to the most severe postbaseline abnormality grade for a given lab test:

- Graded laboratory abnormalities

For all summaries of laboratory abnormalities, the denominator is the number of subjects with nonmissing postbaseline values up to 30 days after last dosing date.

A by-subject listing of treatment-emergent Grade 3 or 4 laboratory abnormalities will be provided by subject ID number and visit in chronological order. This listing will include all test results that were collected throughout the study for the lab test of interest, with all applicable severity grades or abnormal flags displayed.

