7.3. Body Weight and Vital Signs

Body weight and vital signs will not be summarized or listed.

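### Vital signs, a named part of the primary endpoint, get no output, and the by-visit laboratory statistics are dropped without appearing in the visible list of changes in SAP 2.3

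*SAP*

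**What the plan says.** Protocol 8.1.2 defines the primary endpoint as safety and tolerability, evaluated through "treatment-emergent adverse events (TEAEs), including SAEs, clinical laboratory tests, and vital signs assessments at various time points during the study". Two later sections of the protocol set out the matching output:

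- Laboratory tests (Protocol 8.5.3): "Selected laboratory data will be summarized (n, mean, SD, median, Q1, Q3, minimum, and maximum) by study visit", with change from baseline.
- Vital signs (Protocol 8.5.4): "Vital sign measurements and 12-lead ECG data will be summarized by overall and listed by subject".

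The SAP withdraws both. SAP 7.2.1 states "Descriptive statistics for laboratory tests will not be provided", and SAP 7.3 states "Body weight and vital signs will not be summarized or listed".

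SAP 2.3 lists the departures from the protocol, with limited enrolment as the reason. The outputs withdrawn are "part of safety summaries and listings (body weight, vital signs, prior and concomitant medications, electrocardiogram [ECG], and pharmacodynamic parameters) planned in the protocol". Numeric laboratory summaries are not among them. SAP 7.2 meanwhile opens with "Laboratory data collected during the study will be analyzed and summarized using both quantitative and qualitative methods".

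**The concern.** This is a single-arm descriptive study with no formal testing, so its descriptive safety output is its primary result. If a measure named in the primary endpoint appears in no table and no listing, the report cannot speak to that part of the endpoint.

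The laboratory issue is different. Output remains, but the primary objective concerns escalating doses. The by-visit statistics were the planned tabular view that came closest to separating the dose stages, because Weeks 4, 8 and 12 close the 30, 60 and 100 mg stages. Without them, a gradual hepatic or renal drift during escalation that does not raise a toxicity grade has to be found by reading listings. A reader who relies on SAP 2.3 for changes from the protocol would also not learn that these statistics had gone.

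**Working it through.** **1. Planned against provided, by component of the primary endpoint**

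| Component | Protocol plan | Visible SAP output | Removal visible in SAP 2.3? |
|---|---|---|---|
| TEAEs and SAEs | Tables and listings | Kept (SAP 7.1.6) | Not applicable |
| Laboratory tests | By-visit statistics with change from baseline, graded abnormalities | Listings, graded and categorical tables, liver-threshold counts, baseline statistics (SAP 5.2). By-visit numeric statistics dropped | No |
| Vital signs | Summary and listing | None | Yes, citing limited enrolment |

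**2. Vital signs: amount of data without output**

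The Study Procedures Table (Protocol Appendix 2) schedules vital signs at Screening, Day 1, Weeks 1, 4, 8 and 12, and Follow-Up: 7 visits. Footnote g gives 5 measures: heart rate, systolic and diastolic pressure, respiratory rate and temperature.

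- Per subject: 7 × 5 = 35 values.
- The final number of subjects is not given. The target was about 20 and enrolment stopped early. For an assumed 10 to 20 subjects: 35 × 10 = 350 to 35 × 20 = 700 values.
- At one row per visit, the listing has 7 × 10 = 70 to 7 × 20 = 140 rows.

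**3. Laboratory: what the remaining tables can show**

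For treatment-emergent abnormalities, SAP 7.2.2.2 says "subjects will be categorized according to the most severe postbaseline abnormality grade for a given lab test". The single-test liver counts in SAP 7.2.3 likewise use each subject's worst value. Neither separates the dose stages. SAP 7.2.2.2 also has a by-visit summary, but only for laboratory data that are categorical in nature. Even grades tabulated by visit would miss the three shifts below, which use the SAP Appendix 2 grades and the protocol's own formulae.

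(a) *Albumin 2.9 to 2.7 g/dL.* Both values are Grade 2 (below 3, down to 2). In Protocol Table 6-1, albumin of 2.8 to 3.5 scores 2 points and below 2.8 scores 3. The total in the order HE, ascites, bilirubin, albumin, INR goes from 1 + 1 + 1 + 2 + 1 = 6 to 1 + 1 + 1 + 3 + 1 = 7, that is, from class A to class B. A score of 6 is eligible under exclusion criterion 3.

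(b) *Creatinine 0.80 to 1.19 mg/dL, assuming ULN 1.2.* The ratio 1.19/0.80 = 1.49 does not exceed 1.5 × baseline, and 1.19 does not exceed ULN, so the value stays Grade 0. At constant weight and age, Cockcroft-Gault eGFR is proportional to 1/creatinine: 0.80/1.19 = 0.672, so 90 mL/min becomes 60.5 (−32.8%). The limit is 1 − 1/1.5 = 33.3%, reached where 1.5 × baseline is at or below ULN. For assumed ULNs of 1.0 to 1.3, that means baselines up to 1.0/1.5 = 0.67 to 1.3/1.5 = 0.87. eGFR has no grade in SAP Appendix 2.

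(c) *INR 1.21 to 1.50.* Both values are Grade 1 (above 1.2, up to 1.5). With bilirubin and creatinine unchanged, the MELD formula in Protocol 6.8.5 adds 10 × 1.12 × ln(1.50/1.21) = 2.41 points.

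**4. Internal consistency of the SAP**

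SAP 7.2 promises quantitative methods and SAP 7.2.1 removes the numeric summaries. SAP 3.7.2 and Table 3-1 still define visit windows for chemistry, eGFR, hematology and coagulation.

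**The case against.** - **Vital-sign abnormalities can reach the report as adverse events.** Protocol 7.1.3 requires this when they come with signs or symptoms and meet the AE definition. That is true, but such events belong to the adverse-event component. The measurements themselves, and any asymptomatic change, still have no output.
- **The vital-signs removal is declared, with a reason.** This also stands, so the fault is not concealment. Limited enrolment can justify dropping a summary table. It makes a listing shorter, so it is no reason to drop the listing.
- **The laboratory examples are individual shifts that a by-visit mean or median would largely hide, while the by-subject listings would show them.** This is the strongest point. The listings remain, cover eGFR explicitly, and flag values that are out of range or graded. It argues for minimum and maximum change or individual profiles rather than means; it does not justify having no by-visit output. In example (b) the creatinine is neither out of range nor graded, so it would not be flagged.
- **The protocol has its own controls.** Child-Pugh is scored at every visit, and a score of 7 or more triggers confirmation and follow-up (Protocol 7.5.3). Example (a) would therefore be seen during conduct. The gap is in reporting, not in patient protection.
- **The protocol already pools graded abnormalities over all doses, and visit only approximates dose.** This is correct, because escalation depends on tolerability and a re-challenge repeats a stage. It is a reason to show dose alongside visit.
- **Redaction.** Parts of SAP 2.3, and text after 5.3 and after 7.6, are blacked out. Table 3-1 sets windows for Child-Pugh, MELD, chemistry and coagulation, so some by-visit tables may exist there. This limits the laboratory half only.
- **The conflict between SAP 7.2 and 7.2.1 may be template wording.** This is plausible. The rule for values below quantitation also serves the baseline statistics, so it is weak evidence of a contradiction. The two sections still need to agree.

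**Conclusion.** The concern holds and should be fixed. On vital signs, the SAP leaves a named component of the primary endpoint without any output, against Protocol 8.1.2 and 8.5.4. This rests on unredacted text; only the total of 350 to 700 values depends on an assumption, namely 10 to 20 subjects.

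On laboratory tests, the SAP withdraws statistics that Protocol 8.5.3 planned, and the visible list in SAP 2.3 does not say so. The visible tables that remain cannot separate dose stages or show within-grade change. The examples show that such change can be material: one Child-Pugh class, up to a third of eGFR, or 2.4 MELD points. They are constructed illustrations, not observed data. The creatinine example depends on an assumed ULN, and the conclusion for laboratory tests depends on what the redacted sections contain.

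No hypothesis test or sample-size figure is affected.

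**What to change.** 1. Add to SAP 7.3 a by-subject, by-visit listing of vital signs that shows the dose at each visit, with a simple by-visit summary if feasible.
2. Restore by-visit values and change from baseline for a selected set of hepatic and renal analytes: creatinine and eGFR, bilirubin, albumin, INR, platelets, ALT, AST and ALP. With few subjects, n, median, minimum and maximum, or individual profile plots, would be enough if the reduction from the protocol's set is declared.
3. Enter in SAP 2.3, with a reason, any laboratory summary that stays removed. Declaring the removal without restoring anything would correct the record but leave the gap in the view by dose stage.
4. Reword SAP 7.2 and 7.2.1 so that they agree.

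Listings of ECG, body weight and concomitant medication are optional here, because the primary endpoint does not name them.

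The cost is SAP wording and standard outputs on about 20 subjects or fewer, using data already collected. The report grows by a few pages, and by-visit statistics on so few subjects will be imprecise and should be read as descriptive only.

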7.2.2. Graded Laboratory Values

The CTCAE Version 5.0 will be used to assign toxicity grades (0 to 4) to laboratory results for analysis. Grade 0 includes all values that do not meet the criteria for an abnormality of at least Grade 1. For laboratory tests with criteria for both increased and decreased levels, analyses for each direction (ie, increased, decreased) will be presented separately.

For the baseline ALP, total bilirubin, GGT, ALT and AST toxicity grades, the CTCAE version 5.0 will be used to assign grades to the derived average values.

7.2.2.1. Treatment-Emergent Laboratory Abnormalities

Treatment-emergent laboratory abnormalities are defined as values that increase at least 1 toxicity grade from baseline at any postbaseline time point, up to and including the date of last dose of study drug plus 30 days. If the relevant baseline laboratory value is missing, any abnormality of at least Grade 1 observed within the time frame specified above will be considered treatment emergent.

7.2.2.2. Summaries of Laboratory Abnormalities

Laboratory data that are categorical will be summarized using the number and percentage of subjects in the study with the given response at baseline and each scheduled postbaseline visit.

The following summaries (number and percentage of subjects) for treatment-emergent laboratory abnormalities will be provided by lab test; subjects will be categorized according to the most severe postbaseline abnormality grade for a given lab test:

- Graded laboratory abnormalities

For all summaries of laboratory abnormalities, the denominator is the number of subjects with nonmissing postbaseline values up to 30 days after last dosing date.

A by-subject listing of treatment-emergent Grade 3 or 4 laboratory abnormalities will be provided by subject ID number and visit in chronological order. This listing will include all test results that were collected throughout the study for the lab test of interest, with all applicable severity grades or abnormal flags displayed.

7.2.3. Liver-related Laboratory Evaluations

Liver-related abnormalities after initial study drug dosing will be examined and summarized using the number and percentage of subjects who were reported to have the following laboratory test values for postbaseline measurements.

For subjects with normal baseline ALT/AST (\leq ULN):

- Subjects meeting criteria for close observation
 - ALT/AST $> 3 \times$ ULN
- Subjects meeting any one of the following criteria for withholding study drug
 - ALT/AST $> 8 \times$ ULN
 - ALT/AST $> 5 \times$ ULN for 2 weeks
 - ALT/AST $> 3 \times$ ULN and total bilirubin $> 2 \times$ ULN (or direct bilirubin $> 2 \times$ baseline in subjects with Gilbert's syndrome)
 - ALT/AST $> 3 \times$ ULN and INR > 1.5 (if not on anticoagulation)

For subjects with elevated baseline ALT/AST ($>$ ULN)

- Subjects meeting criteria for close observation
 - ALT/AST $> 2 \times$ Baseline or > 300 U/L
- Subjects meeting any one of the following criteria for withholding study drug
 - ALT/AST $> 8 \times$ Baseline or > 500 U/L
 - ALT/AST $> 3 \times$ Baseline or > 300 U/L, and total bilirubin $> 2 \times$ ULN (or direct bilirubin $> 2 \times$ Baseline in subjects with Gilbert's syndrome)
 - ALT/AST $> 3 \times$ Baseline or > 300 U/L, and INR > 1.5 (if not on anticoagulation)

The summary will include data from all postbaseline visits up to 30 days after the last dose of study drug. For individual laboratory tests, subjects will be counted once based on the most severe postbaseline values. For both the composite endpoint of AST or ALT and total bilirubin, subjects will be counted once when the criteria are met at the same postbaseline visit date. The denominator is the number of subjects in the Safety Analysis Set who have nonmissing postbaseline values of all relevant tests at the same postbaseline visit date. A listing of subjects who met at least 1 of the above criteria will be provided.

